6.1.2. Treatment Period Medications and Administration

During the double-blind Treatment Period, subjects will take 1 tablet of study drug (vibegron or matched placebo) once daily for up to 24 weeks. The appearance of the vibegron and placebo tablets will be identical. All subjects will be administered a witnessed dose of study drug at the study site at Visit 3 (Baseline). Subjects in Part 1 additionally will be administered a witnessed dose of study drug at Visit 5 (Week 2) and Visit 6 (Week 4). The date and time of the study drug dosing will be recorded.

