10.7.3. Baseline, Visit 3 (Day 1)

- Assess inclusion/exclusion criteria
- Review concomitant medications*
- Review AEs/SAEs*
- Review and data enter completed Bladder Diary*

- Administer IPSS, [REDACTED] PGI, [REDACTED] scales*
- Record blood pressure (3 results taken 1-2 minutes apart after sitting for 5 minutes), pulse, respiration, temperature, and weight (Part 2 subjects only)
- Record respiration, temperature, and weight at Hour 0, and record triplicate orthostatic blood pressure (sitting blood pressure taken 1-2 minutes apart after sitting for 5 minutes, standing blood pressure taken 1-2 minutes apart within 3 minutes of standing) and orthostatic heart rate (by pulse) measurements at Hour 0 (pre-dose) and 1, 2, 4, and 6 hours (\pm 15 minutes) post-dose (Part 1 subjects only)
- Perform brief physical examination
- If not performed previously (and not available within 6 months prior to Screening), perform urodynamics assessment any time prior to randomization (for sub-study in Part 2 only)
- Measure post-void residual volume
- Perform laboratory assessments
- Dispense double-blind study drug
- Administer witnessed dose of study drug
- Option to dispense paper PRO questionnaires and diaries
- Dispense Bladder Diaries* (for completion at Week 2)

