7.3.2. Orthostatic Blood Pressure and Pulse Rate (Part 1 only)

Blood pressure and pulse rate measurements are collected at Screening, Run-in, Baseline, Week 2 and 4 to assess for potential orthostatic vital sign changes. Triplicate measurements are

obtained for both sitting and standing blood pressure assessments at Hour 0 (pre-dose) and Hours 1, 2, 4, and 6 post-dose. A singular pulse rate is also obtained in sitting and standing positions at the same hourly timepoint. The average blood pressure of triplicates will be used for summary. Within each timepoint, orthostatic blood pressure and pulse rate will be derived by subtracting time-matched standing average values from sitting average values. Then time-matched change from Day 1 will be derived as follows:

- Step 1: calculate change from pre-dose at each visit

CFPre at baseline visit: (Baseline 1 hr – Baseline pre); (Baseline 2hr – Baseline pre)

(Baseline 6 hr – Baseline pre)

CFPre at Week 2 visit: (Week 2 1 hr – Week 2 pre); (Week 2 2hr – Week 2 pre)

(Week 2 6 hr – Week 2 pre)

CFPre at Week 4 visit: (Week 4 1 hr – Week 4 pre); (Week 4 2hr – Week 4 pre)

(Week4 6 hr – Week4 pre)

- Step 2: calculate time-matched from Day 1 by subtracting time-matched CFPr of Baseline visit from CFPr of Week 2 and Week 4

[(Week 2 1 hr – Week 2 pre) - (Baseline 1 hr – Baseline pre)]

[(Week 2 2hr – Week 2 pre) - (Baseline 2 hr – Baseline pre)]

...

[(Week2 6hr – Week2 pre) - (Baseline 6hr – Baseline pre)]

Observed SBP, DBP, and pulse rate will be summarized by treatment, visit and assessment time including corresponding change from baseline value. Baseline is the average of pre-dose measurement at Day 1. The following summary tables will be prepared for derived orthostatic SBP, DBP and pulse rate:

- Time-matched orthostatic parameters by treatment, visit and assessment time
- Time-matched change from Day 1 in orthostatic parameters by treatment, visit and assessment time
- Maximum CFB over 6 hours in orthostatic parameters by treatment and visit
- Average CFB over 6 hours in orthostatic parameters by treatment and visit

In addition, the following plots will be prepared for orthostatic vital sign parameters

- Line plot over time of time-matched change from Day 1 of orthostatic parameters
- Empirical cumulative distribution function of maximum CFB over 6 Hours

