For SBP and DBP, the number and percentage of subjects with a decrease of ≥ 20 mmHg for SBP and ≥ 10 mmHg for DBP from sitting to standing position will also be presented by treatment, visit and assessment time. All orthostatic blood pressure and pulse rate measurements will be listed.

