14.3.1.20 Listing of TEAEs of Special Interest	SAF	
Safety Labs		
14.3.2.1 Hematology Laboratory Parameters	SAF	Include observed and CFB

Title	Population	Programming notes
14.3.2.2 Clinical Chemistry Laboratory Parameters	SAF	Include observed and CFB
14.3.2.3 Urinalysis Laboratory Parameters	SAF	Include observed and CFB
14.3.2.4 Summary of Other Laboratory Parameters	SAF	
14.3.2.5 Abnormal Classification of Hematology Laboratory Parameters	SAF	
14.3.2.6 Abnormal Classification of Clinical Chemistry Laboratory Parameters	SAF	
14.3.2.7 Abnormal Classification of Urinalysis Laboratory Parameters	SAF	
14.3.2.8 Abnormal Classification Summary of Other Laboratory Parameters	SAF	
14.3.2.9 Shift Table of L/N/H Classification for Hematology Laboratory Parameters	SAF	
14.3.2.10 Shift Table of L/N/H Classification for Chemistry Laboratory Parameters	SAF	
14.3.2.11 Maximum Post-baseline ALT and AST vs. Maximum Post-baseline Bilirubin	SAF	
14.3.2.12 Listing of Subjects who Potentially Met Hy's Law	SAF	

Title	Population	Programming notes
Concomitant Medication		
14.3.3.1 Non-OAB Concomitant Medication	SAF	
14.3.3.2 OAB Concomitant Medication	SAF	
Regular and Orthostatic Vital Signs		
14.3.4.1 Vital Sign Parameters	SAF	Include all observed and CFB
14.3.4.2 Vital Sign Parameter Change from Baseline Shifts at 3 Consecutive Visits	SAF	SBP, DBP and PR
14.3.4.3 Vital Sign Parameter Change from Baseline Shifts at Week 24	SAF	SBP, DBP and PR
14.3.4.4 Vital Sign Parameter Maximum Post-Baseline Change from Baseline	SAF	SBP, DBP and PR
14.3.4.5 Orthostatic Blood Pressure and Pulse Rate	SAF-Orth	
14.3.5.1 Time-Matched Change from Sitting to Standing Position in Orthostatic Blood Pressure and Pulse Rate	SAF-Orth	
14.3.5.2 Time-Matched Change from Day 1 in Orthostatic Blood Pressure and Pulse Rate	SAF-Orth	

Title	Population	Programming notes
14.3.5.3 Maximum CFB over 6 Hours in Orthostatic Blood Pressure and Pulse Rate	SAF-Orth	
14.3.5.4 Average CFB over 6 Hours in Orthostatic Blood Pressure and Pulse Rate	SAF-Orth	
14.3.5.5 Categorical Shift from Sitting to Standing in Blood Pressure	SAF-Orth	
Urodynamics		
14.3.6.1 Urodynamics Assessments	SAF-UDS	
Other		
14.3.7.1 Prostate Volume Measurements	SAF	
14.3.8.1 Uroflow Measurements	SAF	
14.3.9.1 Total IPSS score	SAF	
14.3.10.1 Physical Examination Shift from Baseline	SAF	

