11.2.2. Output Figures

Table 10: List of Output Figures

Title	Population	Programming notes
Efficacy Endpoints		
14.2.1.1 Plot of LS Means (SE) of Change from Baseline in Average Number of Daily Micturition Episodes Primary Efficacy Analysis (MMRM)	FAS	Including all visits
14.2.1.2 Forest Plot of Vibegron Treatment Effect vs. Placebo on Average Number of Daily Micturition Episodes at Week 12 by Subgroup Primary Efficacy Analysis (MMRM)	FAS	
14.2.2.1 Plot of LS Means (SE) of Change from Baseline in Average Number of Daily Urgency Episodes Primary Efficacy Analysis (MMRM)	FAS	Including all visits
14.2.2.2 Forest Plot of Vibegron Treatment Effect vs. Placebo on Average Number of Daily Urgency Episodes at Week 12 by Subgroup Primary Efficacy Analysis (MMRM)	FAS	
14.2.3.1 Plot of LS Means (SE) of Change from Baseline in Average Number of Nocturia Episodes per Day (MMRM)	FAS	Including all visits
14.2.4.1 Plot of LS Means (SE) of Change from Baseline in Average Number of Daily Urge Urinary incontinence Episodes (MMRM)	FAS-I	Including all visits

Title	Population	Programming notes
14.2.5.1 Plot of LS Means (SE) of Change from Baseline in International Prostate Symptom Score (IPSS) Storage Score (MMRM)	FAS	Including all visits
14.2.6.1 Plot of LS Means (SE) of Change from Baseline in Volume Voided per Micturition (MMRM)	FAS	Including all visits
Safety Endpoints		
14.3.3.1 Scatter Plot of Maximum ALT Post-Baseline versus Maximum Total Bilirubin Expressed as Multiples of ULN	SAF	
14.3.3.2 Scatter Plot of Maximum AST Post-Baseline versus Maximum Total Bilirubin Expressed as Multiples of ULN	SAF	
14.3.3.3 Line Plot of Liver Chemistry Test Results over Time for Subjects with Elevated ALT or AST, and Elevated Total Bilirubin at Any Time	SAF	Only produce for subjects who potentially met Hy's law
14.3.4.1 Line Plot of Mean (SE) in CFB of Systolic Blood Pressure	SAF	X-axis starts from baseline visit
14.3.4.2 Line Plot of Mean (SE) in CFB of Diastolic Blood Pressure	SAF	X-axis starts from baseline visit
14.3.4.3 Line Plot of Mean (SE) in CFB of Pulse Rate	SAF	X-axis starts from baseline visit
14.3.5.1 Line Plot of Mean (SE) in Time-Matched Change from Day 1 of Orthostatic Systolic Blood Pressure	SAF-Orth	

Title	Population	Programming notes
14.3.5.2	Line Plot of Mean (SE) in Time-Matched Change from Day 1 of Orthostatic Diastolic Blood Pressure	SAF-Orth
14.3.5.3	Line Plot of Mean (SE) in Time-Matched Change from Day 1 of Orthostatic Pulse Rate	SAF-Orth

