14.3.5.4	Empirical Cumulative Distribution Function of Maximum Change from Baseline over 6 Hours to Week 2 and Week 4 Orthostatic Systolic Blood Pressure	SAF-Orth Week 2 and Week 4 CDF plots side-by-side on the same page
14.3.5.5	Empirical Cumulative Distribution Function of Maximum Change from Baseline over 6 Hours to Week 2 and Week 4 Orthostatic Diastolic Blood Pressure	SAF-Orth Week 2 and Week 4 CDF plots side-by-side on the same page
14.3.5.6	Empirical Cumulative Distribution Function of Maximum Change from Baseline over 6 Hours to Week 2 and Week 4 Orthostatic Pulse Rate	SAF-Orth Week 2 and Week 4 CDF plots side-by-side on the same page

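### The time-matched orthostatic change from Day 1 subtracts readings taken after the first double-blind dose, so it can hide or reverse a drug effect; the SAP also drops orthostatic hypotension from its special-interest list

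*SAP*

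**What the plan says.** **Orthostatic derivation.** SAP 7.3.2 first forms the orthostatic parameter at each timepoint as sitting minus standing, so a fall on standing is positive. Step 1 takes the change from the same visit's pre-dose value at Baseline, Week 2 and Week 4. Step 2 reads: "Step 2: calculate time-matched from Day 1 by subtracting time-matched CFPr of Baseline visit from CFPr of Week 2 and Week 4". For the change-from-baseline summaries the same section uses a different reference: "Baseline is the average of pre-dose measurement at Day 1".

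The Step 2 quantity feeds Table 14.3.5.2, "Time-Matched Change from Day 1 in Orthostatic Blood Pressure and Pulse Rate", and Figures 14.3.5.1 to 14.3.5.3, of which the first is "Line Plot of Mean (SE) in Time-Matched Change from Day 1 of Orthostatic Systolic Blood Pressure". The other three orthostatic figures are cumulative distribution plots, described as "Week 2 and Week 4 CDF plots side-by-side on the same page". Falls of at least 20 mmHg systolic or 10 mmHg diastolic "from sitting to standing position will also be presented by treatment, visit and assessment time".

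**Timing of the first dose.** Protocol 6.1.2 has the first double-blind dose given under observation at Visit 3. SAP 4.3.3 defines Day 1 by that dose. Protocol 10.7.3 schedules the Part 1 orthostatic "measurements at Hour 0 (pre-dose) and 1, 2, 4, and 6 hours" post-dose at that visit.

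**Adverse events of special interest.** Protocol 8.4.6 names orthostatic hypotension, confirmed by orthostatic vital signs, as one of these events. Protocol 9.4.3.1 undertakes to summarise the events defined there by treatment group. The list in SAP 7.1 does not contain it.

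**The concern.** A time-matched baseline is normally a drug-free profile, subtracted to remove hour-of-day variation. Here the Day 1 profile is drug-free only in the placebo arm. In the vibegron arm it contains the acute response to the first dose, and Step 1 has already removed anything present before dosing at Week 2 or Week 4. Comparing with placebo does not repair this, because the subtracted drug response exists in one arm only.

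Orthostatic measurement is the main feature that sets Part 1 apart, and Figures 14.3.5.1 to 14.3.5.3 are the only orthostatic line plots planned. A flat or reversed curve could appear beside tables that do show an orthostatic change, and a reader of the figures could take it as reassurance.

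The list omission bears on the same safety question. If the special-interest outputs are built from the SAP 7.1 list, they will lack a category that the protocol undertakes to report.

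**Working it through.** **1. What Step 2 estimates.** Use the SAP's sitting-minus-standing value and let
- d = hour-of-day change shared by both arms and all days;
- e1 = drug effect at hour h on Day 1, after the first dose;
- p = drug effect pre-dose at Week 2;
- e2 = drug effect at hour h at Week 2.

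Vibegron: [(d + e2) - p] - [(d + e1) - 0] = e2 - p - e1.

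Placebo: d - d = 0.

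Step 2 contrast: **e2 - p - e1**. It equals e2 only when e1 + p = 0, for example when both are absent. Week 4 works the same way.

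**2. What change from Day 1 pre-dose estimates.** Vibegron: d + e2. Placebo: d. Contrast: **e2**, whatever e1 and p are.

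**3. Numbers.** The documents give no orthostatic effect size, so these are assumptions: e2 = 10 mmHg and d = 4 mmHg.

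| Day 1 post-dose effect e1 | Week 2 pre-dose effect p | Step 2 contrast | Change from Day 1 pre-dose: vibegron, placebo, difference |
|---|---|---|---|
| 10 | 0 | 0 | 14, 4, 10 |
| 0 | 10 | 0 | 14, 4, 10 |
| 5 | 5 | 0 | 14, 4, 10 |
| 10 | 10 | -10 | 14, 4, 10 |
| 5 | 0 | 5 | 14, 4, 10 |
| 2 | 3 | 5 | 14, 4, 10 |
| 0 | 0 | 10 | 14, 4, 10 |

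The distortion can also go the other way: with e1 = -3 and p = 0, Step 2 shows 10 + 3 = 13.

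**4. What the displays can show.** Three visits (Day 1, Week 2, Week 4) by five hours (0, 1, 2, 4, 6) give 15 points, or 14 after removing the Day 1 pre-dose reference. Step 2 covers 2 visits x 4 hours = 8. It has none of the 4 Day 1 post-dose points and is zero by construction at the 2 later pre-dose points. The cumulative distribution plots cover Weeks 2 and 4 only, so none of the six orthostatic figures shows the Day 1 post-dose response.

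**5. Extent.** Affected are one of six orthostatic tables (14.3.4.5 and 14.3.5.1 to 14.3.5.5) and three of six figures. Part 1 has about 80 men randomised 1:1, or about 40 per arm.

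**6. Precision of the alternative.** For a simple two-arm difference in change, the 95% CI half-width is t(0.975, 78 df) x SD x sqrt(2/40) = 1.991 x 0.2236 x SD = 0.445 x SD. The documents give no SD; for assumed SDs of 8, 12 and 16 mmHg it is 3.6, 5.3 and 7.1 mmHg.

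**7. Special-interest lists side by side.**

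| Category | Protocol 8.4.6 | SAP 7.1 |
|---|---|---|
| Urinary retention | yes | yes |
| Cystitis or urinary tract infection | yes | yes |
| Major cardiac and cerebrovascular events | yes | yes |
| Hypertension | yes | yes |
| Orthostatic hypotension | yes | **no** |
| Raised AST or ALT with drug withheld or stopped | yes | yes |
| Neoplasms | yes | yes |

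SAP Section 9 declares changes on exploratory endpoints, the responder analysis and COVID-19 only.

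**The case against.** The strongest reply is that the plan already contains valid summaries. The orthostatic parameters by visit and hour, the maximum and average change over 6 hours, the distribution plots and the categorical counts do not use Step 2, and the change summaries already use the Day 1 pre-dose baseline. Mean change by arm and hour could be worked out approximately from Table 14.3.5.1. The Step 2 display is titled as a change from Day 1, its formula is printed, and no test rests on it. The DSMB's orthostatic criteria sit in its Charter, and nothing shows that these displays informed the move to Part 2. All of this stands, and it limits the consequence. It does not make the affected line plots a fair picture of the orthostatic effect, and the title does not tell a reader that the Day 1 reference is on drug.

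On the remedy, change from Day 1 pre-dose shown by arm brings back hour-of-day variation, and SAP 7.3.2 does not select orthostatic data for the SAP 4.2.2 ANCOVA. The first point is why the between-arm difference is needed: d cancels in it. The second is a matter of adding the selection. The intervals would number up to 14 x 3 parameters = 42 and should be read descriptively.

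A drug-free Run-in profile might seem the better reference. However, Protocol 8.3.2 and SAP 7.3.2 imply readings through Hour 6 at Run-in, while Protocol 1.1, 4.1 and 10.7.2 indicate pre-dose only. Even with such a profile, keeping Step 1 would leave e2 - p.

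On the omitted category, the events stay in the general treatment-emergent tables and listings, and an eCRF-driven output might keep them. The SAP does not say which source applies.

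**Conclusion.** Both points hold. Step 2 measures how the within-day post-dose response has changed since the first dose. It does not measure the orthostatic effect at Week 2 or Week 4 unless the Day 1 post-dose and later pre-dose effects sum to zero. Otherwise it can understate, cancel, reverse or overstate that effect. The algebra needs only additive effects and a shared hour-of-day pattern; the mmHg values and SDs are illustrative.

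The damage is confined to one descriptive table and three line plots in about 80 men, and a real blood pressure effect could still be seen in the other orthostatic outputs. The special-interest list is one category short of the protocol, without declaration. These should be corrected; neither affects the efficacy conclusions.

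**What to change.** 1. In SAP 7.3.2, base Table 14.3.5.2 and Figures 14.3.5.1 to 14.3.5.3 on change from the Day 1 pre-dose orthostatic value at each hour of Day 1, Week 2 and Week 4. Show each arm, and add the vibegron-minus-placebo difference with its 95% CI at each hour. The SAP 4.2.2 code, which already requests treatment differences with confidence limits, can be run by visit and hour.
2. Keep Step 2, if wanted, as an extra display labelled as the change in post-dose response since the first dose.
3. Restore orthostatic hypotension to the SAP 7.1 list, the special-interest rows of Table 14.3.1.1, and outputs 14.3.1.12, 14.3.1.13 and 14.3.1.20. State whether these outputs follow the SAP list or the eCRF category.

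The cost is SAP wording, re-programming of one table and three plots, and one added category. No new data are needed, and because the reference is Day 1 pre-dose, the conflict over Run-in readings need not be settled first.

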4.1. Overall Design

This is a Phase 3, randomized, double-blind, placebo-controlled, 2-part, parallel-group, multicenter study to evaluate the safety, tolerability, and efficacy of vibegron 75 mg in men with symptoms of OAB on stable doses of pharmacological therapy for BPH. At Baseline, subjects who meet all eligibility criteria are randomized 1:1 to receive either vibegron 75 mg, or placebo in a double-blind fashion. Randomization will be stratified based on baseline average number of micturition episodes per day (≤ 12 vs > 12), alpha blocker use with or without 5-ARI (yes or no), and urinary incontinence (yes or no).

The study consists of two parts: Part 1 (approximately 80 subjects) and Part 2 (approximately 1008 subjects). Part 2 will proceed following review of 4-week safety data (including orthostatic blood pressure results) of all 80 subjects from Part 1 by an independent DSMB. The independent DSMB will review the safety data throughout the entire study. The 2 study parts are of the same overall design as outlined below but with the following exceptions:

- Part 1 includes additional orthostatic blood pressure and heart rate measurements at Screening, Run-in, Baseline, Week 2, and Week 4 to assess for potential orthostatic changes (pre-dose through 6 hours post dose, except pre-dose for Screening and Run-In).
- Part 2 will include a urodynamics sub-study (approximately 60 subjects), which is described in detail in [Section 8.3.7](#).
 - The rate of enrollment into both the main study and the urodynamics sub-study will be closely monitored. In the case of a discrepancy between the estimated date of completion of enrollment in the urodynamics sub-study and the main study, a decision may be made to continue enrolling only those subjects who are willing to participate in the urodynamics sub-study.

Both study parts will consist of a Screening Period (approximately 1 to 4 weeks), a single-blind therapy plus placebo Run-in Period (approximately 2 weeks), and a randomized double-blind Treatment Period (24 weeks).

Study visit schedules: Visit 1 (Screening), Visit 2 (Run-in), Visit 3 (Baseline), Visit 4 (Week 1), Visit 5 (Week 2), Visit 6 (Week 4), Visit 7 (Week 8), Visit 8 (Week 12), Visit 9 (Week 16), Visit 10 (Week 20), and Visit 11 (Week 24) (End of the Treatment). For subjects enrolled in Part 2 after implementation of Protocol Amendment #2, Visit 4 (Week 1) and Visit 9 (Week 16) will be conducted remotely (via telephone or video call).

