 - For subjects with systolic blood pressure \geq 140 mmHg **OR** diastolic blood pressure \geq 90 mmHg at **baseline** (Visit 3):
An increase, compared to baseline (Visit 3) at **2 consecutive visits**, in the average of 3 systolic blood pressures by \geq 20 mmHg **or** 3 diastolic blood pressures by \geq 10 mmHg
 - Initiation or increase in dose of medication for treatment of hypertension in any subject

Note 1: The onset date for an AESI hypertension is the first of the dates when the event meets any of the above criteria.

Note 2: An *AE of “increased blood pressure”* should be recorded if, in the investigator’s opinion, an elevated blood pressure measurement is clinically significant but does not fulfill the above definition for hypertension.

- Adverse events consistent with **orthostatic hypotension** as confirmed by orthostatic vital signs
- **Elevated serum aspartate aminotransferase (AST) or alanine aminotransferase (ALT)** lab value requiring that study drug be temporarily withheld or permanently discontinued (see [Sections 8.4.6.1](#) and [8.4.6.2](#)). To date, no concern regarding drug-induced liver toxicity has been identified; however, the Sponsor is monitoring laboratory data for a potential safety signal, consistent with Food and Drug Administration guidance [[FDA Guidance, 2009](#)].
- **Neoplasms**

Serious AESIs and elevated liver enzymes or bilirubin requiring withholding of study drug (see [Section 8.4.6.1](#)) must be reported within 24 hours of the study site personnel's knowledge of the event by marking the appropriate box on the AE eCRF and assigning the most appropriate category. Additional information should be provided as directed in the eCRF Completion Guidelines. AESIs that also meet the definition of an SAE must be reported as an SAE, as described in [Section 8.4.4](#). Nonserious AESIs should be reported within 72 hours of the site personnel's knowledge, using the AE eCRF.

8.4.6.1. Criteria for Temporary Withholding of Study Treatment in Association with Liver Test Abnormalities

Elevated liver enzymes or bilirubin sufficient to require withholding study medication must be reported **within 24 hours of the study site personnel's knowledge of the event** using AESI specific eCRFs/forms/worksheets provided for the study.

Hepatic enzymes will be monitored in accordance with FDA drug-induced liver injury guidelines [[FDA, 2009](#)].

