1.2. Study Design

1.2.1. Overall Study Design

This is a Phase 3, randomized, double-blind, placebo-controlled, 2-part, parallel-group, multicenter study to evaluate the safety, tolerability, and efficacy of vibegron 75 mg in men with symptoms of OAB on stable doses of pharmacological therapy for BPH. At Baseline, subjects who meet all eligibility criteria are randomized 1:1 to receive either vibegron 75 mg or placebo in a double-blind fashion.

The study consists of two parts: Part 1 (approximately 80 subjects) and Part 2 (approximately 1008 subjects). Part 1 includes additional orthostatic blood pressure and heart rate measurements at Screening, Run-in, Baseline, Week 2, and Week 4 to assess for potential orthostatic changes (pre-dose through 6 hours post dose, except pre-dose for Screening and Run-In), but is otherwise consistent with the schedule for Part 2. Part 2 will proceed following review of 4-week safety data (including orthostatic blood pressure results) of all 80 subjects from Part 1 by an independent Data Safety Monitoring Board (DSMB). Details on tasks and responsibilities, assessments of safety parameters, including orthostatic blood pressure and criteria for defining clinically significant orthostatic events, will be provided in the DSMB Charter. Part 2 will also include a urodynamics sub-study (approximately 60 subjects). The independent DSMB will review the safety data throughout the entire study.

[figure not shown]
Both study parts will consist of a Screening Period (1 to 4 weeks), a single-blind therapy plus placebo Run-in Period (2 weeks), and a randomized double-blind Treatment Period (24 weeks).

Study visit schedules: Visit 1 (Screening), Visit 2 (Run-in), Visit 3 (Baseline), Visit 4 (Week 1), Visit 5 (Week 2), Visit 6 (Week 4), Visit 7 (Week 8), Visit 8 (Week 12), Visit 9 (Week 16), Visit 10 (Week 20), and Visit 11 (Week 24) (End of the Treatment).

Subjects who complete the Week 24 Visit may be offered the opportunity to enroll in a 28-week extension study URO-901-3006, which will be conducted under a separate study protocol. Subjects who do not enroll into the extension study will have a Safety Follow-up contact approximately 5 days (\pm up to 2 days) after the subject's last dose of study treatment (i.e., or approximately 5 days (\pm up to 2 days) after withdrawal for subjects who discontinue the study early). Additionally, Unscheduled Visit(s) may be arranged as needed.

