1.2.2. Randomization and Blinding

Randomization will occur centrally using an interactive web response system (IWRS) using central, stratified block randomization. Randomization will be stratified based on the following stratification factors:

- Baseline average micturition episodes per day (≤ 12 vs > 12), and
- Alpha blocker use with or without 5-ARI (with vs without), and
- Urinary Incontinence (yes vs no)

Part 1 and Part 2 excluding the urodynamics sub-study will use the same stratified block randomization list. In order to ensure balanced treatment assignment within the urodynamics sub-study a separate randomization list with the same stratification factors and the block size will be used for subjects enrolled in the sub-study.

For this study in the double-blind treatment phase a double-blind/masking technique will be used: vibegron and its matching placebo will be packaged identically so that treatment blind/masking is maintained. The patient, the Investigator, and Sponsor personnel or delegate(s) who are involved in the treatment or clinical evaluation of the patients will not be aware of the treatment group assignments.

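### The Part 1 orthostatic tables show threshold falls only hour by hour, so the final analysis has no prespecified count of men per arm with at least one post-dose fall

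*SAP*

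**What the plan says.** Protocol 4.1 adds serial sitting and standing readings in Part 1 "to assess for potential orthostatic changes". Under SAP 7.3.2, triplicate sitting and standing blood pressures are taken at Hour 0 and at Hours 1, 2, 4 and 6. The visits are Screening, Run-in, Baseline, Week 2 and Week 4.

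For threshold falls, SAP 7.3.2 plans "the number and percentage of subjects with a decrease of ≥ 20 mmHg for SBP and ≥ 10 mmHg for DBP", and this change "from sitting to standing position will also be presented by treatment, visit and assessment time". The matching output in SAP 11.2.1 is Table 14.3.5.5, "Categorical Shift from Sitting to Standing in Blood Pressure", in the SAF-Orth set. It is the only categorical orthostatic table.

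The other orthostatic outputs are continuous: time-matched values, time-matched change from Day 1, maximum and average change from baseline over 6 hours by visit, line plots, and empirical distribution plots of the maximum.

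Protocol 8.4.6 makes orthostatic hypotension "as confirmed by orthostatic vital signs" an adverse event of special interest.

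**The concern.** The simplest question that Part 1 can answer is how many men in each arm had an orthostatic fall after dosing. The planned tables do not answer it. A man who falls at Hours 1, 2 and 4 of one visit appears in three places, and a man who falls once appears in one. The reader cannot tell three falls in one man from one fall in each of three men, so the hourly counts cannot be added up to men.

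Inclusion criterion 4 requires every man to be on an alpha-blocker. It is therefore also natural to ask how many men had a fall after dosing who had none just before the first double-blind dose. That within-man split is not planned either.

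At stake is how the Part 1 safety data will read in the final report. A modest excess spread over many small overlapping rows is hard to see, and similar-looking rows may be taken as reassurance that they cannot give. Without a prespecified per-man count, its definition would be chosen after unblinding.

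**Working it through.** **Inputs from the documents**
- Part 1 has about 80 men (SAP 1.2.1), "randomized 1:1 to receive either vibegron 75 mg or placebo in a double-blind fashion". That gives 80 / 2 = about 40 per arm. The split is approximate, since "Part 1 and Part 2 excluding the urodynamics sub-study will use the same stratified block randomization list", and SAF-Orth may hold fewer.
- Post-dose timepoints on double-blind drug: 3 visits (Day 1, Week 2, Week 4) × 4 hours = 12. If SBP and DBP are shown in separate rows, 12 × 2 = 24 rows.
- The documents give no fall rate and no power for these data, so there is no figure of the plan's own to reproduce.

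**Does another planned output supply the count?**
SAP 7.3.2 derives the orthostatic value as sitting minus standing, with Day 1 pre-dose as baseline. Two illustrations for SBP:
- Pre-dose fall 18 mmHg, post-dose fall 22 mmHg: change = 22 − 18 = 4 mmHg. The man crosses the 20 mmHg threshold but shows a small change.
- Pre-dose rise of 10 mmHg (value −10), post-dose fall 8 mmHg: change = 8 − (−10) = 18 mmHg. The change is large but no threshold is crossed.

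Maximum change therefore does not identify threshold crossings. It is also given per visit and per parameter. SAP 7.3.1.2 does plan an any-post-baseline count for ordinary blood pressure and heart rate, but 7.3.2 has no equivalent.

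**What a per-man row would add (assumed rates)**
- One row: falls in each arm are Binomial(40, p). Power is the total probability of the tables with two-sided Fisher p ≤ 0.05.
- Any of 12 timepoints: logit P(fall | u) = a + s·u, with u standard normal and a set so that the average rate is p. The share of men with any fall is 1 − E[(1 − P(fall | u))^12].
- Between-man SD s is assumed to be 1.5 or 2.5.

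| Rate per timepoint, placebo vs vibegron | s | Men with any fall | Power, one row | Power, per man |
|---|---|---|---|---|
| 4% vs 10% | 1.5 | 28% vs 50% | 6% | 44% |
| 4% vs 10% | 2.5 | 20% vs 37% | 6% | 31% |
| 4% vs 8% | 1.5 | 28% vs 44% | 2% | 24% |
| 4% vs 8% | 2.5 | 20% vs 32% | 2% | 17% |

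The model uses one rate for both a single-parameter row and the SBP-or-DBP composite. These are different events, so the contrast is indicative only.

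A second model (24 looks, equicorrelated latent normal, correlation 0.3 to 0.9, 5% vs 10% per look, normal approximation) gives 20% to 46% per man against 13% for one row.

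**Precision of the proposed row**
- 28% vs 50%: 1.96 × √(0.28 × 0.72/40 + 0.50 × 0.50/40) = 1.96 × 0.106 = 0.21. The difference is 22 points, 95% CI about 1 to 43.
- 20% vs 37%: 1.96 × √(0.20 × 0.80/40 + 0.37 × 0.63/40) = 1.96 × 0.099 = 0.19. The difference is 17 points, 95% CI about −2 to 36.

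**The case against.** The strongest reply is that the table is descriptive. No test is planned, so power per row is not a property of the plan, and the rates behind it are assumed. That stands. A reader might infer that every row is nearly powerless, but that is too strong: at 5% versus 30% one row has 82% power by Fisher's test. The figures describe modest excesses of low rates. The proposed row also remains imprecise, because about 40 men per arm is the limiting factor.

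A reader might also infer that this table weakened the decision to open Part 2. The documents do not support that. The decision followed DSMB review, with orthostatic event criteria in a DSMB Charter and analyses in a separate DSMB SAP (SAP 1.2.1 and 2.1). Neither is available, so whether the DSMB had a per-man count cannot be determined. Table 14.3.5.5 belongs to the final analysis after database lock.

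Two further inferences go too far. Pre-dose falls are not hidden: Hour 0, Screening and Run-in are timepoints, so their frequencies appear by arm, and only the within-man split is missing. Nor is it settled that SBP and DBP falls are shown separately. The sentence in SAP 7.3.2 does not say whether they are separate rows or a joint criterion, and no table shell is given.

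The other outputs help in part. Maximum and average change over 6 hours pool the hours within a man at each visit, so a shift would not be visible only in the hourly rows. Adverse event tables count each man once per preferred term, but they depend on an event being reported, and the list of events of special interest in SAP 7.1 leaves out orthostatic hypotension. All readings are listed, so the count could be made later, but without a definition fixed in advance.

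**Conclusion.** The point holds as a gap in the prespecified final-analysis outputs. Threshold falls are planned only by treatment, visit and assessment time. No output gives the number of men per arm with at least one post-dose fall, and that number cannot be recovered from the planned tables.

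It is a cheap improvement and not a flaw in inference. It does not touch the efficacy analyses. Under the assumed 4% versus 10% per timepoint, the per-man count raises power from about 6% to between 31% and 44%. For a true doubling, 4% versus 8%, it raises power from about 2% to between 17% and 24%. These sizes rest on 40 men per arm, 12 completed timepoints and the assumed between-man SDs. The per-man count is the more informative summary, but a null result from it would still not exclude a material excess.

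**What to change.** In SAP 7.3.2 and Table 14.3.5.5:

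1. Add a lead row: number and percentage of men per arm with an SBP fall of at least 20 mmHg **or** a DBP fall of at least 10 mmHg from sitting to standing, at any post-dose time on Day 1, Week 2 or Week 4. Give the risk difference (vibegron minus placebo) with its 95% CI.
2. Add a second row with the same count, limited to men without such a fall at the Day 1 pre-dose reading.
3. Keep the hourly rows as supporting detail, and state whether they show SBP and DBP separately or jointly.

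The change needs SAP wording and two rows from data already collected. It should be fixed before unblinding; if that has passed, label the rows post hoc in the study report.

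The drawbacks are modest. An any-time count has a higher background rate in both arms. It also depends on how many timepoints each man completed, so the number completed per arm should be shown beside it. Precision remains limited by about 40 men per arm.
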